#### Secondary outcomes

- ! Early definitive treatment rate in 2019 vs. 2020: defined as treatment in accordance with the current guidelines (cholecystectomy or ERCP with endoscopic sphincterotomy during the same hospital admission or within 2 weeks of discharge)
- ! 30-day hospital readmission rate in 2019 vs. 2020: defined as hospital readmission within 30days from discharge for recurrent biliary AP while awaiting interval cholecystectomy, or due to post-cholecystectomy complications
- ! Predictive factors of morbidity and mortality in patients with biliary AP

The compliance of surgeons to the most up-to-date international guidelines on biliary AP will be assessed through the analysis of the following attitudes:

! Use of scoring systems for the diagnosis and severity grading of biliary AP

- ! Use of lipase dosage (for the diagnosis) and CRP (for the severity grading) during the diagnostic workup
- ! Use of Ultrasound scan, CT scan, MRCP, and endoscopic Ultrasound scan (EUS) in the correct way and timing
- ! Use of early ERCP and sphincterotomy in case of cholangitis and/or choledocholithiasis
- ! Use of percutaneous and/or endoscopic drainage in case of infected pseudocyst or necrosis
- ! Timing of surgical necrosectomy
- ! Timing of re-laparotomy in case of open abdomen strategies
- ! Use of prophylactic antibiotics/antifungals
- ! Use of somatostatin analogs
- ! Use of early enteral feeding
- ! Use of early definitive treatment strategies, including cholecystectomy and/or ERCP and sphincterotomy

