## Section 10 – 30-day Morbidity

- ! Gastric outlet obstruction (Yes/No)
- ! Pseudocyst (Yes/No)
- ! Infected necrosis (Yes/No)
- ! Endoscopic drainage of pseudocyst/walled-off necrosis (Yes/No)
- ! CT-guided fine needle aspiration in case of infected pseudocyst/walled-off necrosis (Yes/No)
- ! Surgical necrosectomy (Yes-laparoscopic/Yes-open/No)
- ! Timing of surgical necrosectomy (< 2 weeks from the onset of symptoms/2-4 weeks)>4 weeks)
- ! Setting of surgical necrosectomy (Upfront/After failure of endoscopic necrosectomy/After failure of endoscopic and percutaneous necrosectomy)
- ! Cystogastrostomy (Yes-endoscopic/Yes-surgical/No)
- ! Abdominal compartment syndrome (Yes/No)
- ! Open abdomen (Yes/No)
- ! Timing of re-exploration (24-48 hours/48-72 hours/>72 hours)
- ! Bleeding (Yes/No)
- ! Bowel ischemia (Yes/No)

- ! Bowel fistula (Yes/No)
- ! Necrotizing cholecystitis (Yes/No)

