21. Surgical strategy	
 
! In infected pancreatic necrosis, percutaneous drainage as the first line of treatment (step-up approach) delays the surgical treatment to a more favorable time or even results in complete resolution of infection in 25–60% of patients and it is recommended as the first line of treatment (1A).
 
! Minimally invasive surgical strategies, such as transgastric endoscopic necrosectomy or videoassisted retroperitoneal debridement (VARD), result in less postoperative new-onset organ failure but require more interventions (1B).
 

	
 
! Considering mortality, there is insufficient evidence to support open surgical, mini-invasive, or endoscopic approach (1B).
 
! In selected cases with walled-off necrosis and in patients with disconnected pancreatic duct, a single stage surgical transgastric necrosectomy is an option (2C).
 

	! A multidisciplinary group of experts should individualize surgical
	treatment taking local expertise into account (2C)
22. Timing of cholecystectomy	
 
Laparoscopic cholecystectomy during index admission is recommended in mild acute gallstone pancreatitis (1A).
 
When ERCP and sphincterotomy are performed during the index admission, the risk for recurrent pancreatitis is diminished, but same admission cholecystectomy is still advised since there is an increased risk for other biliary complications (1B).
 
In acute gallstone pancreatitis with peripancreatic fluid collections, cholecystectomy should be deferred until fluid collections resolve or stabilize and acute inflammation ceases (2C).
 

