BEST PRACTICE ADVICE 6	Pancreatic debridement should be avoided in the early, acute period (first 2 weeks), as it has been associated with increased morbidity and mortality. Debridement should be optimally delayed for 4 weeks and performed earlier only when there is an organized collection and a strong indication.
BEST PRACTICE ADVICE 7	Percutaneous drainage and transmural endoscopic drainage are both appropriate first-line, nonsurgical approaches in managing patients with walled-off pancreatic necrosis (WON). Endoscopic therapy through transmural drainage of WON may be preferred, as it avoids the risk of forming a pancreatocutaneous fistula.

BEST PRACTICE ADVICE 8	Percutaneous drainage of pancreatic necrosis should be considered in patients with infected or symptomatic necrotic collections in the early, acute period (<2 weeks), and in those with WON who are too ill to undergo endoscopic or surgical intervention. Percutaneous drainage should be strongly considered as an adjunct to endoscopic drainage for WON with deep extension into the paracolic gutters and pelvis or for salvage therapy after endoscopic or surgical debridement with residual necrosis burden.
BEST PRACTICE ADVICE 9	Self-expanding metal stents in the form of lumen-apposing metal stents appear to be superior to plastic stents for endoscopic transmural drainage of necrosis.
BEST PRACTICE ADVICE 10	The use of direct endoscopic necrosectomy should be reserved for those patients with limited necrosis who do not adequately respond to endoscopic transmural drainage using large-bore, self-expanding metal stents/lumen-apposing metal stents alone or plastic stents combined with irrigation. Direct endoscopic necrosectomy is a therapeutic option in patients with large amounts of infected necrosis, but should be per- formed at referral centers with the necessary endoscopic expertise and interventional radiology and surgical backup.
BEST PRACTICE ADVICE 11	Minimally invasive operative approaches to the debridement of acute necrotizing pancreatitis are preferred to open surgical necrosectomy when possible, given lower morbidity.

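### The CRF cannot record percutaneous drainage, so compliance with the drainage item cannot be measured as written

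*Combined protocol and SAP*

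**What the plan says.** The list of compliance attitudes under Secondary outcomes has eleven entries. One of them is "Use of percutaneous and/or endoscopic drainage in case of infected pseudocyst or necrosis". Either route satisfies it.

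The data for this item should come from CRF Section 10 (30-day Morbidity). That section holds these relevant fields:

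- drainage: "Endoscopic drainage of pseudocyst/walled-off necrosis (Yes/No";
- needle sampling: "CT-guided fine needle aspiration in case of infected pseudocyst/walled-off necrosis (Yes/No";
- setting of surgical necrosectomy, with the options "Upfront/After failure of endoscopic necrosectomy/After failure of endoscopic and percutaneous necrosectomy";
- cystogastrostomy, endoscopic or surgical;
- pseudocyst and infected necrosis, each Yes/No.

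The protocol's guideline tables give the percutaneous route a prominent place. Table 1 (WSES 2019), item 21, opens with "In infected pancreatic necrosis, percutaneous drainage as the first line of treatment (step-up approach" and recommends it as such. The table of the 2015 Japanese guidelines (item 15) and Table 5 (AGA necrosis update, Advice 7) put percutaneous and endoscopic drainage side by side as first-line approaches. The UK 2005 and AGA 2018 tables do not name percutaneous drainage as first line.

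The Primary objective asks which guideline items, when disregarded, go with negative outcomes. The Statistical analysis section plans logistic models that include clinical attitudes as predictors. Neither section says how an attitude is scored from CRF fields or what counts as disregarded.

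**The concern.** A named compliance item needs a route of treatment that the form does not ask about. Two patients with infected necrosis, one drained percutaneously and one not drained, would both be entered as No on the drainage field. Once the form is closed, no model can separate them.

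At stake are two uses of the item: the compliance rate, which is a secondary objective, and its association with death and morbidity, which is the primary objective. The item has to be left out or scored from one route only. In the second case, some patients treated in line with the tabled recommendations would be counted as departures from them.

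**Working it through.** **Step 1. Is percutaneous drainage recorded anywhere?** I read CRF Sections 1 to 14 for a field that would record it.

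- The drainage field names the endoscopic route only.
- Fine needle aspiration is not a substitute. Tables 1 and 2 describe it as obtaining material for Gram stain or culture.
- Neither cystogastrostomy option is percutaneous.
- The only percutaneous wording is the necrosectomy-setting option "After failure of endoscopic and percutaneous necrosectomy". It concerns necrosectomy, applies only to patients who reach surgery, and requires endoscopic failure as well. Surgery after failed percutaneous drainage alone has no accurate code.
- The pseudocyst field does not record infection, so the denominator of the item is incomplete too.

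Result: no section has a percutaneous-drainage field.

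**Step 2. Effect on the compliance rate.** The plan gives no figure for this item, so there is nothing to reproduce. Among patients with an indication, let e be the share drained endoscopically (with or without percutaneous drainage), p the share drained percutaneously only, and u the share not drained, with e + p + u = 1.

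- Compliance with both routes recorded: e + p.
- Compliance scored from the endoscopic field: e.
- Shortfall: p.

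With assumed e = 0.40, p = 0.30 and u = 0.30, compliance is 70% but would be recorded as 40%. Of the recorded No answers, 0.30 / (0.30 + 0.30) = 50% were in fact drained. For p of 10%, 30% or 50%, the shortfall is 10, 30 or 50 percentage points.

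**Step 3. Effect on the mortality odds ratio.** Let mE, mP and mU be mortality in the three groups, and compare not drained with drained.

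- Both routes recorded: odds(mU) / odds(mD), where mD = (e·mE + p·mP) / (e + p).
- Endoscopic field only: odds(mN) / odds(mE), where mN = (p·mP + u·mU) / (p + u).

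Example with e = 0.40, p = 0.30, u = 0.30 and mortality 15/30/15%:

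- mD = (0.06 + 0.09) / 0.70 = 21.4%, so the odds ratio is 0.176 / 0.273 = 0.65.
- mN = (0.09 + 0.045) / 0.60 = 22.5%, so the odds ratio is 0.290 / 0.176 = 1.65.

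The documents give none of these mortalities or shares, so all are assumptions. With e held at 0.40, the odds ratio changes as follows (both routes recorded → endoscopic field only):

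| mE / mP / mU | p = 0.10 | p = 0.30 | p = 0.50 |
|---|---|---|---|
| 20 / 20 / 40% | 2.67 → 2.32 | 2.67 → 1.71 | 2.67 → 1.22 |
| 15 / 30 / 40% | 3.04 → 3.52 | 2.44 → 3.05 | 2.19 → 2.63 |
| 15 / 30 / 15% | 0.80 → 1.20 | 0.65 → 1.65 | 0.58 → 2.15 |
| 20 / 10 / 20% | 1.14 → 0.90 | 1.34 → 0.71 | 1.48 → 0.53 |
| 20 / 20 / 20% | 1.00 → 1.00 | 1.00 → 1.00 | 1.00 → 1.00 |

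The rows show dilution, inflation, reversal in each direction, and no change. These are crude associations. Correct recording removes the misclassification but not confounding by indication.

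**Step 4. How many patients?** The Background puts necrotizing disease at up to 20% of acute pancreatitis. Applied to the minimum sample of 2 × 200 = 400, that is at most 0.20 × 400 = 80, of whom only some have infected necrosis. Infected pseudocysts would add to this. The documents give neither count.

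**The case against.** A reader might infer that guideline-concordant patients are stored as undrained and that their deaths are then charged to non-compliance. The documents do not support that. The form stores the absence of endoscopic drainage, which is a true statement about these patients. It becomes non-compliance only if an analyst scores an either-route item from one route, and no such rule is written. The item could equally be declared not assessable. This objection stands.

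A reader might also infer that disregarding the item is bound to look harmful, because Table 5, Advice 8, places percutaneous drainage "in those with WON who are too ill to undergo endoscopic or surgical intervention". But Advice 7 of the same table calls both routes first line, and Table 1 recommends the percutaneous route for infected necrosis in general. The severity of percutaneously drained patients relative to the others is not settled, and Step 3 shows that the sign depends on it. This stands too.

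The planned models are multivariable, and the CRF collects severity scores, Atlanta class, organ failure and ICU admission. Adjustment may reduce a distortion driven by severity, but it cannot restore the missing route. This part does not rescue the item.

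Finally, this is one of eleven attitudes, listed under Secondary outcomes, and it concerns a subset. The 2019 versus 2020 comparisons of 30-day mortality and morbidity do not use it. That limits the reach of the point but does not make the item measurable.

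**Conclusion.** The point holds in a limited form. The protocol names percutaneous drainage in a compliance item and tables it as first line, alone in one guideline table and jointly with endoscopic drainage in two. The CRF cannot record it. As written, compliance with this item is not measurable, and analysis cannot recover it without going back to the charts. That conclusion needs no assumption.

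The size of the error is conditional on scoring from the endoscopic field. Measured compliance then falls by exactly the percutaneous-only share, which the documents do not give. The mortality odds ratio can move either way or not at all. A claim of spurious harm from disregarding the item would need assumed mortalities that the documents do not supply. Only patients with infected collections are affected. The gap is worth closing because the item feeds the primary objective and the remedy is a few answer codes.

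**What to change.** Keep the existing endoscopic drainage field, which also covers sterile collections, and add to CRF Section 10:

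1. *Percutaneous drainage of pancreatic collection*: Yes/No, with timing from onset.
2. A necrosectomy-setting code: *After failure of percutaneous drainage alone*.
3. Pseudocyst infection status: *No / Sterile / Infected*.

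Pre-specify in the Statistical analysis section that drainage by either route meets the item. Take the denominator and timing from the tabled guideline statements once the sponsor has reconciled where they differ. Table 1 (item 18) refers to deterioration with signs or strong suspicion of infected necrosis. The Japanese table (item 15) ties intervention to an aggravated general condition and, if possible, to the time after 4 weeks. Table 5 (Advice 5) states that drainage and/or debridement is indicated in infected necrosis. Until these are reconciled, an infected collection not drained within the 30-day window should not automatically count as non-compliant.

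If the fields cannot be added before data entry closes on 31/08/2021, report the item as not assessable and do not score it from the endoscopic field.

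The cost is a little more chart abstraction, plus a re-query of records already entered with a collection. The re-query may be harder than usual, because the Data collection section excludes patient identifiers and the protocol describes no linkage key.

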#### Primary objective

! To evaluate which items of the current AP guidelines, if disregarded, correlate with

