#### **Primary outcomes**

- ! 30-day mortality: assessed by the number of AP patients with biliary etiology deceased during the non-pandemic period (2019) and the Covid-19 pandemic period (2020)
- ! 30-day morbidity: assessed by the number of AP patients with biliary etiology who experienced any type of AP-related complication within 30-days from the hospital admission during the non-pandemic period (2019) and the Covid-19 pandemic period (2020)

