#### Section 4 – Clinical Scores

- ! Glasgow Coma Scale (GCS)
- ! qSOFA
- ! WSES (World Society of Emergency Surgery) sepsis score
- ! BISAP (Bedside Index of Severity in Acute Pancreatitis) score
- ! ASA score (1-2-3-4-5)
- ! Glasgow-Imrie score
- ! Ranson's score
- ! Apache II score
- ! Revised Atlanta Classification (Mild acute pancreatitis/Moderately severe acute pancreatitis/Severe acute pancreatitis)
- ! Organ failure during the hospital stay (None/Cardiovascular/Respiratory/Renal)

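### Three of the eleven compliance items, drainage above all, cannot be validly related to 30-day morbidity, because being eligible for the item already makes morbidity Yes, always for drainage and often for the two timing items

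*Combined protocol and SAP*

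**What the plan says.** - Primary objective: "To evaluate which items of the current AP guidelines, if disregarded, correlate with" negative outcomes, by clinical presentation.
- Primary outcomes: 30-day morbidity counts patients "who experienced any type of AP-related complication within 30-days from the hospital admission". No component list follows, and no other section says which CRF fields set morbidity to Yes.
- Analyzed Data (CRF): the main source is "Section 10 – 30-day Morbidity", which has 16 fields. Some are complications. Others are procedures or their attributes, for example "Endoscopic drainage of pseudocyst/walled-off necrosis (Yes/No".
- Secondary outcomes: 11 attitudes measure compliance. They include "Use of percutaneous and/or endoscopic drainage in case of infected pseudocyst or necrosis", "Timing of surgical necrosectomy" and the timing of re-laparotomy under an open-abdomen strategy.
- Statistical analysis: logistic models relate morbidity and mortality to clinical attitudes and to clinical, laboratory and radiological variables. No item is limited to the patients to whom it applies.
- CRF Section 4 holds "Organ failure during the hospital stay (None/Cardiovascular/Respiratory/Renal" as an undated field outside Section 10.

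**The concern.** The primary objective needs an exposure (a guideline item followed or disregarded) and an outcome that can differ between exposed and unexposed patients. For three items both come from the same CRF section, and for drainage the condition that makes a patient eligible is itself a component of the outcome. A model of morbidity on that item then reports how the groups were formed, and says nothing about whether following the guideline helped. The rationale section says the study should provide the basis for care bundles, so an artefact here could be read as evidence for or against a recommendation.

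Two related gaps matter less. The plan does not say whether in-stay organ failure counts as morbidity. Nor does it say how to classify a patient who dies before a late local complication could appear, and a complications-only derivation would record such a patient as having no morbidity.

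**Working it through.** The plan states no figure for any association between an item and morbidity, so there is none to reproduce. The check is a field count, followed by the probability of morbidity among each item's eligible patients.

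**1. Fields in Section 10**

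| Type | Fields | n |
|---|---|---|
| Complication | gastric outlet obstruction; pseudocyst; infected necrosis; abdominal compartment syndrome; bleeding; bowel ischemia; bowel fistula; necrotizing cholecystitis | 8 |
| Procedure, timing or setting | endoscopic drainage; fine needle aspiration; necrosectomy; its timing; its setting; cystogastrostomy; open abdomen; re-exploration timing | 8 |

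Three of the 16 fields match a compliance item directly: endoscopic drainage, necrosectomy timing and re-exploration timing. Adding the closely related fields (necrosectomy, its setting, cystogastrostomy, open abdomen) gives 7 of 16. All of them feed the same 3 of 11 items (27%).

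**2. Drainage among eligible patients**

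Let E be eligibility, D drainage and M morbidity. E requires an infected pseudocyst or infected necrosis, so the pseudocyst or the infected-necrosis field is Yes.
- If all Section 10 fields count: D = 1 sets M = 1, and E = 1 does so as well.
- If only the eight complications count: E = 1 still sets M = 1.

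Under both readings P(M | E, D) = P(M | E, not D) = 1.00. The odds ratio is (1/0)/(1/0), which is undefined.

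**3. Drainage in the whole cohort**

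The documents give no rates for this step. Assume that a share q = 3% to 10% has infected necrosis, that another complication occurs independently at r = 10% to 30%, and that 60% of eligible patients are drained.

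- Drained against everyone else: P(M | D) = 1.00, and P(M | not D) = [0.4q + (1 − q)r] / (1 − 0.6q).
  - Low rates: (0.012 + 0.097)/0.982 = 0.11.
  - High rates: (0.04 + 0.27)/0.94 = 0.33.
- Eligible but undrained against everyone else: P(M | undrained) = 1.00, and P(M | rest) = [0.6q + (1 − q)r] / (1 − 0.4q).
  - Low rates: (0.018 + 0.097)/0.988 = 0.12.
  - High rates: (0.06 + 0.27)/0.96 = 0.34.

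The first coding makes drainage look harmful and the second makes its omission look harmful. Both odds ratios are infinite. That result does not depend on q, r or the 60%.

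**4. The two timing items**

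Table 1, item 19 lists abdominal compartment syndrome, bleeding, bowel ischaemia, necrotizing cholecystitis and bowel fistula as indications for surgery, and all five are Section 10 complications. For these, and for infected necrosis, M = 1 whatever the timing. Table 5, advice 5 also allows debridement in some patients with sterile necrosis, which is not a Section 10 complication. Morbidity is therefore not fixed at Yes for every necrosectomy patient.

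**5. Necrosectomy timing against 30-day mortality**

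The latest timing category is more than 4 weeks from symptom onset, so a patient in it was alive at about day 28. If admission falls a days after onset, a 30-day window from admission closes on day 30 + a. That leaves about (30 + a) − 28 = 2 + a days in which a death could be counted. Late surgery would look protective by construction.

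**6. Size of the eligible group**

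The Background gives necrotizing disease in up to 20% of cases, with 38% of those needing intervention. The Sample size section gives a minimum of 2 × 200 = 400 patients. Then 400 × 0.20 × 0.38 = 30.4 patients. At the 15% mortality quoted for necrotizing disease, that is 30.4 × 0.15 = 4.6 deaths. These rates describe acute pancreatitis of any cause, and infected pseudocysts without necrosis are not in the figure.

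**The case against.** The best reply is that Primary outcomes speaks of complications, and a necrosectomy or an aspiration is not one. The CRF groups fields loosely elsewhere too: Section 9 puts ERCP under concomitant findings. This stands as far as it goes. That performing a procedure itself sets morbidity to Yes is inferred from the section heading only. But the reply does not rescue the drainage item, because step 2 gives the same result when only complications count.

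Several stronger readings are tempting, and the documents do not support them.

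- A reader might infer that half of Section 10 is scored as compliance. Only 3 fields match directly, or 7 on a broad reading. Fine needle aspiration is diagnostic and absent from the list of attitudes.
- A reader might infer that all three items are wholly degenerate. Sterile necrosis prevents that for necrosectomy timing.
- A reader might infer that organ failure is excluded from morbidity, so that up to 20% of patients would be missed. The wording "any type of AP-related complication within 30-days from the hospital admission" can include organ failure. The 20% would also require that no patient with organ failure has any of the eight complications.
- A reader might infer that up to 30% of severe patients die unrecorded. That would require every such death to precede any complication. The Background instead names infected necrosis as the main driver of late mortality, and Table 1 places the highest risk of death in organ failure combined with infected necrosis. Deaths are also counted in the other primary outcome.

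What remains of the last two is that the rules for organ failure and early death are not written down.

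**Conclusion.** The point holds for 3 of the 11 compliance items and one of the two primary outcomes. For drainage the failure is complete: the odds ratio is undefined among eligible patients, and in the whole cohort it is an artefact whose direction depends on coding. For necrosectomy timing and re-laparotomy timing it holds whenever the indication is a listed complication (infected necrosis, abdominal compartment syndrome, bowel ischemia and the like).

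The drainage conclusion rests on the eligibility wording and the Section 10 field list alone. It needs no assumed rate and no view on whether procedures count as morbidity. The figure of about 30 eligible patients is a ceiling at the planned minimum size and uses the Background's rates.

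The other eight items, which are collected outside Section 10, are not affected by this overlap. Neither are 30-day mortality and the 2019 versus 2020 mortality comparison. A reader might infer that the primary objective as a whole fails, and the documents do not support that.

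**What to change.** 1. State that 30-day morbidity is Yes if any of the eight complication fields is Yes, and that no procedure, timing or setting field contributes. Say whether in-stay organ failure counts. If it does, use the field as recorded: it carries no date and does not separate new from pre-existing failure, so new failure within 30 days cannot be derived from it. Organ failure also marks severity in this document, so including it overlaps with any severity strata.
2. Do not model the three items against the morbidity composite. Analyse drainage and re-exploration timing in eligible patients only, with 30-day mortality as outcome. Report necrosectomy timing descriptively or with a landmark analysis.
3. Add a sensitivity composite of death or any complication within 30 days, so that early deaths do not count as freedom from morbidity.

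Moving fields between CRF sections is unnecessary, since it changes no variable. Two limits of the fields should be stated: the pseudocyst field does not record infection, and percutaneous drainage has no Yes/No field of its own. As it stands, the drainage analysis can identify eligible patients securely only through infected necrosis, and it sees endoscopic drainage only. Drainage is also undated, so some survival bias remains.

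The cost is a short addition to the outcome definition and the Statistical analysis section, plus one sensitivity analysis. Three items lose a morbidity result that would be invalid or largely so. With at most about 30 eligible patients and about 5 deaths at the minimum sample size, the replacement analyses should be labelled exploratory.
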